### **11.3. Efficacy Analyses**

The primary efficacy endpoint, time to all-cause discontinuation of study drug, will be estimated by the Kaplan-Meier method and summarized (number of discontinuations, number of censored subjects, median, 25th and 75th percentile, if estimable) by treatment group. Time to all-cause discontinuation of study drug is defined as the number of days from the first dose of study drug to the last dose of study drug. Subjects who complete treatment are not considered to have discontinued. A stratified log-rank test (stratified for baseline insomnia status) will be used to test the hypothesis that there is no difference between the JNJ-42847922 group and quetiapine XR in the probability of discontinuing study drug, using a 1-sided 0.10 significance level.

The analyses for the secondary efficacy endpoints will be described in the SAP. For all other efficacy endpoints, no multiplicity adjustment will be done and nominal p-values will be presented.

#### **11.4. Biomarker Analyses**

Cortisol levels will be tabulated for each time point and summary statistics will be calculated. Post-treatment changes in cortisol levels will be assessed by treatment group. Analysis of variance (ANOVA) and t-test will be used to assess differences across groups and time points. Correlations between cortisol levels and clinical endpoints will be evaluated.

The additional exploratory biomarkers will be tabulated by treatment and summary statistics will be calculated. Post-treatment changes in exploratory biomarkers will be summarized by treatment group. Associations between baseline biomarker levels and clinical endpoints may be explored. Additional exploratory analyses may also be performed. Results of all exploratory analysis will be presented in a separate report.

All biomarker data obtained from this study may also be included in an ongoing cross-study analysis to investigate the relationship between depression severity, phenotypes, and biomarkers.

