
 
• To assess the effect of JNJ-42847922 compared to quetiapine XR as adjunctive therapy for MDD on hormonal stress-response via HPA axis function.
 
	
 
• Change from baseline to Weeks 6 and 24 in salivary cortisol levels as measured at home upon awakening and at home during the evening.
 

 
• To assess the safety and tolerability of JNJ-42847922 compared with quetiapine XR as adjunctive treatment in subjects with MDD.
 
	
 
• Safety assessments including:               
 
– Adverse events (AEs).
 
– Proportion of all SAEs and events of special interest (eg, parasomnias).
 
– Vital signs, physical examinations, ECG, and laboratory parameters.
 
– Sexual functioning using the Arizona Sexual Experiences Scale (ASEX).
 
– Extrapyramidal symptoms assessed by the Extrapyramidal Symptom Rating Scale-Abbreviated (ESRS-A).
 
– Suicidality assessed using the C-SSRS.
 
– Potential withdrawal effects assessed by the Physician Withdrawal Checklist (PWC).
 
 
 

Exploratory	

 
• To collect medical resource utilization (MRU) data that may be used in future economic modeling.
 
	
 
• Healthcare Resource Use Questionnaire (HRUQ).
 

 
• To assess the effect of JNJ-42847922 compared with quetiapine XR as adjunctive therapy for MDD on self-reported measures of sleep.
 
	
 
• Change from baseline in subjective sleep parameters as measured by the Consensus Sleep Diary-Morning Administration (CSD-M) after the first 6 weeks of treatment (using the average of 3 morning measurements in Week 6).
 
• Change from baseline in subjective sleep parameters as measured by the CSD-M after 3 to 6 months of treatment (using
 

Objectives	Endpoints

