- A urine sample will be collected and sent to the central laboratory to assess compliance with the following background antidepressant medications: citalopram, escitalopram, fluvoxamine, fluoxetine, paroxetine, sertraline, and venlafaxine. All other SSRI/SNRI background antidepressants qualifying the subject for enrollment will be assayed (urine or blood sample) locally at the study site, if possible.
- Minimum criteria for the availability of documentation supporting the eligibility criteria are described in Section 17.4, Source Documentation.
- Subjects will administer the assigned study drug once daily at bedtime, approximately 3 hours after the last meal, from Day 1 to Day 167. Subjects are required to record the administration of study drug or any missed doses in subject diaries, which will be checked at each scheduled visit.
- Serum or urine pregnancy tests may be performed, as determined necessary by the investigator, to establish the absence of pregnancy at any time during the subject's participation in the study. A FSH test may also be performed at investigator judgment to assist in determining if a woman is of non-childbearing potential.
- Blood sample should be collected in fasting condition (at least 8 hours fasting). The serum chemistry also includes fasting glucose and insulin.
- FT4 analysis will be performed for subjects with known hypothyroidism who have been on stable treatment for at least 3 months prior to screening and otherwise for any subject with an elevated TSH.
- Where multiple procedures are scheduled for the same visit, procedures are recommended to be performed in the following order: ECGs, vital signs, blood draws, PRO assessments and then other procedures.
- Salivary cortisol samples (morning and evening) will be collected by subjects at home. Evening salivary cortisol samples (ie, on Days -1, 13, 41, 83, and 167) will be collected pre-dose, at bedtime. The morning sample will be collected upon awakening (ie, on Days 1, 14, 42, 84, and 168). Subjects should not consume alcoholic beverages for at least 12 hours prior to saliva sampling. Food, drinks (except water), and oral care (brushing, flossing, mouthwash) are not permitted 1 hour prior to the saliva collection.

- m. Biomarker samples should be collected under fasting conditions. Subjects should not participate in strenuous exercise or consume alcohol for 24 hours prior to collection.

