
 
To assess the effect of JNJ-42847922 compared to quetiapine XR as adjunctive therapy for MDD on hormonal stress-response via HPA axis function.
 
	
 
Change from baseline to Weeks 6 and 24 in salivary cortisol levels as measured at home upon awakening and at home
 

Objectives	Endpoints

 
To assess the safety and tolerability of JNJ-42847922 compared with quetiapine XR as adjunctive treatment in subjects with MDD.
 
	
during the evening.
 
 
Safety assessments including: 
 
Adverse events (AEs).
 
Proportion of all SAEs and events of special interest (eg, parasomnias).
 
Vital signs, physical examinations, ECG, and laboratory parameters.
 
Sexual functioning using the Arizona Sexual Experiences Scale (ASEX).
 
Extrapyramidal symptoms assessed by the Extrapyramidal Symptom Rating Scale-Abbreviated (ESRS-A).
 
Suicidality assessed using the C-SSRS.
 
Potential withdrawal effects assessed by the Physician Withdrawal Checklist (PWC).
 
 
 

Exploratory	

 
To collect medical resource utilization (MRU) data that may be used in future economic modeling.
 
	
 
Healthcare Resource Use Questionnaire (HRUQ).
 

 
To assess the effect of JNJ-42847922 compared with quetiapine XR as adjunctive therapy for MDD on self-reported measures of sleep.
 
	
 
Change from baseline in subjective sleep parameters as measured by the Consensus Sleep Diary-Morning Administration (CSD-M) after the first 6 weeks of treatment (using the average of 3 morning measurements in Week 6).
 
Change from baseline in subjective sleep parameters as measured by the CSD-M after 3 to 6 months of treatment (using the average of 3 morning measurements in Weeks 12, 18, and 24, respectively).
 

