## **5. TREATMENT ALLOCATION AND BLINDING**

### **Treatment Allocation**

#### ***Procedures for Randomization and Stratification***

Central randomization will be implemented in this study. Subjects will be randomly assigned to 1 of 2 treatment groups based on a computer-generated randomization schedule prepared before the study by or under the supervision of the sponsor. The randomization will be balanced by using randomly permuted blocks and will be stratified by insomnia status (significant insomnia symptoms [ISI score  $\geq 15$ ] at baseline versus no significant insomnia symptoms [ISI score  $< 15$ ] at baseline).

The interactive web response system (IWRS) will assign a unique treatment code, which will dictate the treatment assignment and matching study drug kit for the subject. The requestor must use his or her own user identification and personal identification number when contacting the IWRS, and will then give the relevant subject details to uniquely identify the subject.

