### **10.2. Withdrawal From the Study**

Because the primary endpoint of this study is time to all-cause discontinuation, investigators should ensure that appropriate withdrawal criteria have been met when withdrawing a subject from the study, especially when subjects are withdrawn due to lack of efficacy. The investigator should complete a detailed summary of the discontinuation, including the reasons for withdrawal and time of the withdrawal, in the CRF and in the source document. If the withdrawal results from an AE, the clinical course of the AE and the outcome (recovered, resolving, or ongoing) of the AE should be documented.

A subject will be automatically withdrawn from the study for any of the following reasons:

- Lost to follow-up
- Withdrawal of consent
- Death
- Noncompliance with study drug administration (ie, missing either 4 or more consecutive doses of study medication or a total of 20 or more doses during the 6-month period)
- Investigator's impression of noncompliance with background antidepressant therapy
- Discontinuation of study treatment for any reason. A subject's study treatment will be automatically discontinued if:
  - The investigator or sponsor believes that for safety reasons or tolerability reasons (eg, AE) it is in the best interest of the subject to discontinue study treatment
  - The subject becomes pregnant
  - The subject shows signals of acute suicidal ideation with a clear plan at any time during the study; the subject should be referred to appropriate medical/psychiatric care

- AST and/or ALT exceeds 5 x Upper Limit of Normal (ULN) (confirmed by repeat testing)
- AST and/or ALT exceeds 3 x ULN and total bilirubin exceeds 1.5 x ULN (confirmed by repeat testing).

If a subject withdraws from the study before the end of the double-blind phase (ie, Day 168), end-of-study/follow-up assessment should be obtained.

If a subject is lost to follow-up, every reasonable effort must be made by the study-site personnel to contact the subject and determine the reason for discontinuation/withdrawal. The measures taken to follow-up must be documented. If a subject leaves the study due to withdrawal of consent, the investigator will make sure that there is not a reason for the withdrawal of consent such as lack of efficacy or poor tolerance (ie, due to an AE).

Study drug assigned to the withdrawn subject may not be assigned to another subject. Subjects who withdraw will not be replaced.

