8. BIOMARKERS

Details of the biomarker analysis are provided in a separate document.

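### For salivary cortisol, a comparative secondary endpoint, the protocol states only ANOVA and t-tests on change, with no baseline covariate, insomnia stratum or explicit repeated-measures structure

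*Protocol*

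**What the plan says.** **Endpoint.** Protocol 2.1 and the synopsis list as secondary "Change from baseline to Weeks 6 and 24 in salivary cortisol levels as measured at home upon awakening and at home during the evening". The objective it serves is a comparison of JNJ-42847922 with quetiapine XR on HPA-axis function. SAP 1.1 repeats the endpoint.

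**Method.** Protocol 11.4 says "Post-treatment changes in cortisol levels will be assessed by treatment group" and then "Analysis of variance (ANOVA) and t-test will be used to assess differences across groups and time points". The synopsis carries the same sentences. Neither place names a covariate, a stratification term, a within-subject correlation structure or a rule for missing samples.

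**Data collected.** The Time and Events Schedule footnote says "Evening salivary cortisol samples (ie, on Days -1, 13, 41, 83, and 167) will be collected pre-dose, at bedtime", with morning samples on the following days. That gives a baseline and four on-treatment occasions: Weeks 2, 6, 12 and 24. No cortisol is scheduled at the end-of-study visit.

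**Randomisation.** Protocol Section 5: "The randomization will be balanced by using randomly permuted blocks and will be stratified by insomnia status".

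**Leaving the study.** Protocol 10.2 lists the grounds for automatic withdrawal from the study. One entry begins "Discontinuation of study treatment for any reason. A subject's study treatment will be automatically discontinued if". A subject who stops study drug therefore has no later scheduled cortisol sample.

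**SAP.** Section 1 excludes biomarker analyses and Section 8 says "Details of the biomarker analysis are provided in a separate document". Cortisol appears neither in the visit-window table nor among the efficacy variables in Table 4.

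**The concern.** The cortisol comparison carries the trial's secondary objective on stress-hormone response, yet its stated method is thinner than that of nearly every other continuous scale.

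- The SAP applies the 5.3.1.2 MMRM, with each scale's own baseline and insomnia status, to HAM-A, QLDS, PROMIS-SD, PROMIS-SRI, SMDDS, SDMT, TMT-Part B and MADRS-6.
- CGI-S and PGI-S get a rank ANCOVA with the same two terms.
- Two exploratory measures, the sleep diary and MADRS-WOSI, also get the MMRM.
- HVLT-R, which is summarised descriptively only, is the exception.

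Two things are at stake. The first is precision that the collected baseline would supply at no cost. The second is the Week 24 comparison: a plain t-test there takes nothing from subjects who have left, in arms that the sample-size assumptions expect to lose subjects at different rates.

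**Working it through.** **1. Reproduce the plan's own figure.** Inputs from Protocol 11.2: 50 subjects per arm, 50% discontinuing on quetiapine XR, hazard ratio 0.415, one-sided 0.10.

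- Implied discontinuation on JNJ-42847922 under proportional hazards: 1 − (1 − 0.50)^0.415 = 0.25.
- Expected events: 50 × 0.50 + 50 × 0.25 = 37.5.
- Power (Schoenfeld): Φ(√(37.5 × 0.25) × |ln 0.415| − 1.2816) = Φ(1.41) = 0.921.

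This matches the stated 92%, so the 50% and 25% rates can be carried forward. The 92% concerns the primary endpoint only; the documents give no SD, correlation or power for cortisol.

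**2. Cost of leaving baseline out as a covariate.** Assume equal variance σ² at baseline and follow-up, and correlation r between them. For each arm, the variance contribution in units of σ² is 2(1 − r) for an unadjusted change and 1 − r² with baseline as a covariate. Their ratio is 2(1 − r)/(1 − r²) = 2/(1 + r). Because r is not documented, a range is shown.

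| Assumed r | Change score, 2(1 − r) | Adjusted, 1 − r² | Ratio, 2/(1 + r) |
|---|---|---|---|
| 0.2 | 1.60 | 0.96 | 1.67 |
| 0.3 | 1.40 | 0.91 | 1.54 |
| 0.5 | 1.00 | 0.75 | 1.33 |
| 0.6 | 0.80 | 0.64 | 1.25 |
| 0.8 | 0.40 | 0.36 | 1.11 |

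The unadjusted change comparison would need 11% to 67% more subjects for the same precision. The formula is a large-sample one and ignores the degree of freedom spent on the covariate.

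**3. Who is left at Week 24.** On quetiapine XR, 50 × (1 − 0.50) = 25. On JNJ-42847922, 50 × (1 − 0.25) = 37.5. The total is 62.5 of 100. Relative to 50 against 50, information is (1/50 + 1/50)/(1/25 + 1/37.5) = 0.0400/0.0667 = 0.60, so the standard error is 1/√0.60 = 1.29 times as large. The Week 2, 6 and 12 samples of the other 37.5 subjects play no part in a Week 24 t-test.

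**4. Illustration.** Suppose a true difference of 0.5 SD (an assumption) at two-sided 0.20, which corresponds to the SAP's 80% intervals, with 25 and 37.5 subjects. Power is Φ(0.5/√(v × 0.0667) − 1.2816), where v is the entry from the table in step 2.

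- r = 0.2: 0.60 unadjusted, 0.76 adjusted.
- r = 0.5: 0.74 unadjusted, 0.83 adjusted.
- r = 0.8: 0.96 unadjusted, 0.97 adjusted.

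These figures reflect baseline adjustment alone. Any gain from the stratum term or from earlier visits is not quantified, because the documents give nothing to base it on.

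**The case against.** The strongest objection is that the operative analysis is out of sight. Protocol Section 11 describes itself as general and leaves detail to the SAP, and the SAP passes biomarkers to another document. Covariates, correlation structure and missing-data handling are what such a document would settle. This stands as a limit on the point: a reader might infer that the final cortisol analysis is unadjusted, and the documents cannot show that. It does not remove the protocol's stated method. If the biomarker plan already has a better model, the protocol text should agree with it or refer to it.

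Other inferences also go too far:

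- *That baseline is ignored.* It is not. The endpoint and 11.4 both work with change, so baseline enters by subtraction. What is missing is covariate adjustment.
- *That repeated visits are ignored.* ANOVA across groups and time points could mean a repeated-measures ANOVA. The sentence does not say, and the t-test named beside it has no such structure.
- *That a completers-only rule has been set.* None is stated. The restriction at Week 24 follows from the withdrawal rule, the sampling schedule and the nature of a t-test.

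It is also fair to say that an unadjusted change comparison is a legitimate choice in a randomised trial, that this is an exploratory Phase 2 study with no power target for cortisol, and that the SAP does not impose the MMRM on every scale. The loss described here is one of efficiency and specification.

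**Conclusion.** The point holds as one of under-specification and avoidable imprecision. For a comparative secondary endpoint, the only stated method omits baseline cortisol as a covariate, the randomisation stratum and an explicit repeated-measures structure, although the data for all three are collected.

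The size is a variance 1.11 to 1.67 times that of a baseline-adjusted analysis for r from 0.8 to 0.2, under equal variances. At Week 24 a t-test would rest on about 25 against 37 subjects. That count assumes the plan's 50% rate, hazard ratio 0.415, proportional hazards, and samples from everyone who remains.

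A reader might expect an MMRM to repair the Week 24 comparison. It would not create Week 24 values for those who left. It would use their earlier samples under a missing-at-random assumption, and the unequal dropout would remain. Confidence that the protocol text is deficient is high; confidence that the final analysis shares the deficiency is limited by the missing biomarker document.

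**What to change.** In Protocol 11.4, the synopsis and the biomarker plan, replace the ANOVA and t-test sentence with text to this effect:

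*Change from baseline in morning and in evening salivary cortisol will be analysed separately with the MMRM of SAP 5.3.1.2, with treatment, visit (Weeks 2, 6, 12 and 24), treatment-by-visit interaction, baseline insomnia status, and the corresponding baseline cortisol as covariate. The treatment difference and its 80% confidence interval will be reported at Weeks 6 and 24. The analysis assumes data missing at random; the number of subjects contributing at each visit will be shown by arm.*

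If the biomarker plan already contains such a model, refer to it from the protocol and remove the conflicting sentence.

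A log scale is optional. The documents give no cortisol distribution, and logs would turn the effect into a ratio. If it is considered, decide before unblinding on the pooled distribution. Protocol Section 5 keeps cortisol data from the sponsor's study team until after database lock, so either someone outside that team makes the check or the scale is fixed in advance.

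The cost is wording and reuse of an existing model. No sample, visit or subject is added.

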#### **11.5. Pharmacokinetic Analyses**

Concentration-time data will be summarized using descriptive statistics by dose, visit date and time (relative to dose) for JNJ-42847922, and metabolites M12 and M16 (as applicable).

#### **11.6. Pharmacogenomic Analyses**

Individual predicted post-hoc Bayesian estimates of PK parameters will be used in exploratory exposure-genetic variant modeling, as appropriate. Results of other exploratory genetic/epigenetic analyses will be presented in a separate report.

#### **11.7. Medical Resource Utilization and Health Economics Analyses**

Medical resource utilization and health economics will be descriptively summarized by treatment group.

#### **11.8. Safety Analyses**

##### **Adverse Events**

The verbatim terms used in the CRF by investigators to identify AEs will be coded using the Medical Dictionary for Regulatory Activities (MedDRA). Treatment-emergent adverse events are adverse events with onset during the double-blind treatment phase or that are a consequence of a preexisting condition that has worsened since baseline. All reported TEAEs will be included in the analysis. For each TEAE, the percentage of subjects who experience at least 1 occurrence of the given event will be summarized by treatment group.

Summaries, listings, datasets, or subject narratives may be provided, as appropriate, for those subjects who die, who discontinue treatment due to an AE, or who experience a severe or a serious adverse event.

Adverse events of special interest are cataplexy, sleep paralysis, and complex, sleep-related behaviors (parasomnias). Subjects with adverse events of special interest may be presented separately.

### **Clinical Laboratory Tests**

Laboratory data will be summarized by type of laboratory test and treatment. Reference ranges and markedly abnormal results (specified in the SAP) will be used in the summary of laboratory data. Descriptive statistics will be calculated for each laboratory analyte at baseline and for observed values and changes from baseline at each scheduled time point. A listing of subjects with any laboratory results outside the reference ranges will be provided. A listing of subjects with any markedly abnormal laboratory results will also be provided.

The homeostatic model assessment will be conducted to estimate changes in beta-cell function and insulin sensitivity based on insulin and glucose laboratory values.

### **Electrocardiogram (ECG)**

A listing of subjects with abnormal ECG findings will be presented.

### **Vital Signs**

Descriptive statistics of pulse, supine and standing blood pressure (systolic and diastolic), and temperature for observed values and changes from baseline will be summarized at each scheduled time point by treatment. The percentage of subjects with values beyond clinically important limits will be summarized.

### **Physical Examination**

Physical examination findings will be summarized at each scheduled time point. Changes in body weight and waist circumference will be summarized descriptively. Subjects with abnormal findings in physical examination will be presented in a data listing.

### **Columbia Suicide Severity Rating Scale (C-SSRS)**

Results from the C-SSRS will be tabulated by treatment.

### **Physicians Withdrawal Checklist (PWC)**

Results from the PWC will be tabulated by treatment.

### **Arizona Sexual Experiences Scale (ASEX)**

Results from the ASEX will be tabulated by treatment.

### **Extrapyramidal Symptom Rating Scale—Abbreviated (ESRS-A)**

Results from the ESRS-A will be tabulated by treatment.

